## **Study Procedures**

### **Retrospective Analysis (January 1, 2024 – December 30, 2024)**

Collect baseline and clinical data from patients who underwent thoracic surgery at Tongji Hospital and its affiliated campuses, including sex, age, occupation, past medical history, symptoms and onset time, complete blood count, liver and kidney function, blood gas analysis, coagulation profile, and postoperative inflammatory markers.

Analyze the association between intraoperative paravertebral block (PVB) and postoperative thoracic complications.

### **Prospective Analysis (Mar 2025 – May 2028)**

Screen patients meeting the inclusion criteria and immediately collect baseline data, including sex, age, occupation, past medical history, symptoms and onset time, vital signs, MMP3 levels, complete blood count, liver and kidney function, blood gas analysis, coagulation profile, and postoperative inflammatory markers.

Record postoperative outcomes at 24 and 48 hours, including cough and pain scores, time to first flatus and defecation, length of hospital stay, and the incidence of 30-day postoperative complications, including pulmonary infection, respiratory failure, pleural effusion, atelectasis, bronchospasm, pneumothorax, aspiration-induced lung injury, pulmonary embolism, bronchopleural fistula, and acute respiratory distress syndrome (ARDS).

Evaluate the association between PVB and MMP3 levels with postoperative thoracic complications and validate these findings against the results of the retrospective analysis.

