## Study Design

This study is an **observational investigation combining both retrospective and prospective components**, targeting patients undergoing thoracic surgery, primarily pulmonary and mediastinal procedures.

**Retrospective component:** Data will be collected from patients across multiple campuses of Tongji Hospital who previously underwent thoracic surgery with intraoperative paravertebral block (PVB). These cases will be retrospectively analyzed to examine the association between PVB and postoperative complication reduction.

**Prospective component:** For patients enrolled prospectively, perioperative biochemical parameters—including **MMP3, neutrophils, leukocytes, procalcitonin (PCT), C-reactive protein**

**(CRP)**, and other relevant regulatory factors—will be measured preoperatively and postoperatively. Postoperative outcomes will be assessed by recording **cough and pain scores**, as well as **time to first flatus and defecation** at 24 and 48 hours after surgery. Additionally, the incidence of postoperative complications will be followed up for **30 days postoperatively**.

**Clinical correlation:** The association between the measured biomarkers and patient outcomes will be systematically evaluated to determine their clinical relevance in predicting prognosis and postoperative recovery.

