## **Potential Risks and Risk Mitigation**

This study is an observational investigation combining retrospective and prospective components and is associated with minimal to no adverse reactions or direct risks to participants. The collection of clinical data and postoperative laboratory results is solely for statistical analysis and does not alter standard clinical care, ensuring no significant risk to patients.

The study strictly adheres to applicable laws and regulations, with all patient medical information treated as confidential. Necessary measures are implemented to ensure data security, and patient information will never be disclosed, sold, or used unlawfully, thereby protecting patient privacy and rights.

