## **Data Collection and Statistical Analysis**

Data will be collected and verified by three study personnel to ensure accuracy and reliability. The variables to be recorded are as previously described. Statistical analyses will be performed using R software version 4.4.

**Within-group comparisons:** Quantitative variables will be analyzed using paired t-tests or Wilcoxon one-sample tests.

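### Cough and pain have no preoperative score, so a non-randomised PVB comparison of the 24 h and 48 h scores can be adjusted only crudely for preoperative severity

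*Protocol*

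**What the plan says.** Two sections of the protocol time the cough and pain scores, and they agree. Study Design places them "at 24 and 48 hours after surgery", and the prospective part of Study Procedures says "Record postoperative outcomes at 24 and 48 hours, including cough and pain scores". Neither adds a preoperative time point.

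The biochemical markers are treated differently: Study Design says that they "will be measured preoperatively and postoperatively".

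Baseline collection in the prospective part begins "Screen patients meeting the inclusion criteria and immediately collect baseline data". The items that could reflect existing cough or pain are in the run "past medical history, symptoms and onset time, vital signs, MMP3 levels". No scale or severity grade is attached to the symptoms.

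The study is an "observational investigation combining both retrospective and prospective components", and Potential Risks and Risk Mitigation says that data collection "does not alter standard clinical care". Data Collection and Statistical Analysis states that the variables recorded are those already described, so the list above is the full list.

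**The concern.** Patients awaiting lung or mediastinal surgery may already cough or have chest pain, and the exclusion criteria do not remove those with chronic cough or chronic pain. The study does not assign PVB, so the groups need not start level. If they differ before surgery, some of that difference will carry into the 24 h and 48 h scores and could be read as an effect of the block.

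The usual remedy is to adjust for the same score taken before surgery. That value is not collected and cannot be recovered afterwards. A statistical analysis plan can choose covariates only from what was recorded, so this is a matter for the protocol.

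The scores matter to the study's reasoning. The Background argues that better pain control lets patients breathe deeply and cough, and so lowers pulmonary complications. A confounded pain comparison would weaken the evidence for that step.

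**Working it through.** **What is available at each time**

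| | Before surgery | 24 h | 48 h |
|---|---|---|---|
| Biochemical markers | measured | postoperative, hour not fixed | postoperative, hour not fixed |
| Cough score, pain score | none | scored | scored |
| Symptoms with onset time | recorded, unscored | – | – |

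For cough and pain, the only same-scale difference that can be formed is 48 h minus 24 h, and both values come after the block and the operation. The multivariable models listed under Effect analysis could include a symptom-present indicator or its duration, but not preoperative severity.

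**Size, on assumed values.** No figure in the protocol bears on this point; its sample size of 57 comes from an ROC calculation. The inputs below are therefore assumptions, apart from N = 252, which is the total stated in Sample Size Estimation.

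- d = 0.3: difference in mean preoperative score between PVB groups, in SD units.
- r: correlation of preoperative with postoperative score within groups, from 0.1 to 0.6. Low values are plausible if most patients score near zero before surgery or if early pain comes mainly from the operation.
- No true PVB effect, and a linear relation between the two scores.

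Formulas: spurious contrast = r × d; residual variance after adjustment = 1 − r²; effective sample-size factor relative to no adjustment = 1/(1 − r²).

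| r | r × 0.3 (SD) | 1 − r² | 1/(1 − r²) |
|---|---|---|---|
| 0.1 | 0.03 | 0.99 | 1.01 |
| 0.3 | 0.09 | 0.91 | 1.10 |
| 0.5 | 0.15 | 0.75 | 1.33 |
| 0.6 | 0.18 | 0.64 | 1.56 |

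**What this does to a test.** Assume further that half of the patients receive PVB and that the test is two-sided at 0.05. With N = 252 the standard error is √(4/252) = 0.126 SD. At r = 0.5 the spurious contrast is 0.15/0.126 = 1.19 standard errors. The chance of a false positive is Φ(1.19 − 1.96) + Φ(−1.19 − 1.96) ≈ 0.22 instead of 0.05. At r = 0.1 the ratio is 0.03/0.126 = 0.24, and the same formula gives about 0.06.

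**A limit on the precision gain.** The last column of the table assumes balanced groups. With d = 0.3 and half receiving PVB, adjustment also multiplies the variance by 1 + 0.25 × 0.3² = 1.0225. At r = 0.1 this cancels the 1% gain (1.01/1.0225 = 0.99); at r = 0.6 the factor becomes 1.56/1.0225 = 1.53. The stronger reason for a baseline score is therefore less confounding. Precision is a gain only when r is moderate or high.

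**The case against.** Postoperative-only scoring is stated consistently in both places, with no contradiction and no wrong figure. That is correct, so this is an improvement in data collection and not an error in the text.

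Three stronger readings are tempting, and the documents support none of them.

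- *Existing cough or pain cannot be separated from the effect of the block at all.* A reader might infer this from the missing score. But symptoms with onset time and past medical history are collected at baseline, and multivariable regression is planned. Adjustment or stratification by the presence of a symptom is possible. What is missing is severity on the same scale.
- *The study's main question is compromised.* The Objective, and the PVB analyses stated in Study Procedures, concern postoperative complications. No section names a PVB comparison of cough or pain; it is only implied by the general between-group tests. The complication outcome does not depend on a baseline cough or pain score.
- *The paired tests are unusable.* The line "Quantitative variables will be analyzed using paired t-tests or Wilcoxon one-sample tests" is general. The markers measured before and after surgery give it a natural use, and nothing assigns it to cough or pain.

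It can also be objected that no section says how PVB is chosen. That is so. Non-random use follows from the observational design and unchanged care, but a baseline imbalance is a possibility, not an established fact. Finally, the comparison with no adjustment overstates the gain to the extent that the symptom record already does part of the work.

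**Conclusion.** The point holds within these limits. For cough and pain, which are secondary in that the Objective names only complications, a PVB comparison can be adjusted only crudely for preoperative severity, and change from baseline on the same scale cannot be computed. The 30-day complication analysis is untouched.

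The size is not known from the documents. With an assumed imbalance of 0.3 SD, the spurious contrast runs from 0.03 SD (r = 0.1) to 0.18 SD (r = 0.6), and the effective sample-size gain over no adjustment from about 1% to 56%, less the small imbalance penalty shown above. At the low end the omission hardly matters; at the high end it could mislead. Even a scored baseline removes only the confounding that it carries, not other reasons for giving or withholding the block. The change is worth making because it is cheap and the value cannot be obtained later.

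**What to change.** In the prospective part of Study Procedures, add to the baseline list a preoperative cough score and a preoperative pain score, on the same scales as at 24 h and 48 h and taken at the screening contact. State that when PVB groups are compared on the 24 h and 48 h scores, the matching preoperative score enters as a covariate: in a linear model if the scale is treated as continuous, in an ordinal model if it is ordinal. Keep the symptom and onset record.

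The cost is about a minute per patient and two form fields, with no extra visit or procedure. Patients enrolled before the change will lack the scores and have only the symptom record, so the report should show how many there are and how they were handled. Prospective collection is scheduled from March 2025 to May 2028, and the earlier the change is made, the fewer they will be.

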## **Potential Risks and Risk Mitigation**

This study is an observational investigation combining retrospective and prospective components and is associated with minimal to no adverse reactions or direct risks to participants. The collection of clinical data and postoperative laboratory results is solely for statistical analysis and does not alter standard clinical care, ensuring no significant risk to patients.

The study strictly adheres to applicable laws and regulations, with all patient medical information treated as confidential. Necessary measures are implemented to ensure data security, and patient information will never be disclosed, sold, or used unlawfully, thereby protecting patient privacy and rights.

## **Data Collection and Statistical Analysis**

Data will be collected and verified by three study personnel to ensure accuracy and reliability. The variables to be recorded are as previously described. Statistical analyses will be performed using R software version 4.4.

**Within-group comparisons:** Quantitative variables will be analyzed using paired t-tests or Wilcoxon one-sample tests.

### **Between-group comparisons:**

Quantitative variables: analyzed using repeated measures ANOVA or Mann-Whitney U tests.

Qualitative variables: analyzed using Pearson's  $\chi^2$  test.

Ordinal variables: analyzed using Wilcoxon rank-sum tests.

### **Descriptive statistics:**

Continuous variables: presented as mean  $\pm$  standard deviation (SD) and confidence intervals (CI); when necessary, minimum, maximum, 25th percentile, median, and 75th percentile will be reported.

Paired continuous variables: differences reported as mean  $\pm$  SD.

Non-parametric data: reported as median and mean ranks.

Categorical variables: presented as frequency distributions and percentages.

Ordinal variables: presented as frequency distributions, percentages, median, and mean ranks.

Binary/qualitative variables: reported as positivity rate, number of positive cases, and total sample size.

**Diagnostic evaluation:** When appropriate, the area under the receiver operating characteristic curve (AUC) will be calculated to assess the predictive value of ultrasound parameters.

**Effect analysis:** Associations and predictive effects will be evaluated using correlation analysis, multivariable linear regression, logistic regression, Cox proportional hazards models, and Kaplan-Meier survival analysis.

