## Sample Size Estimation

As this study is an observational investigation, the final sample size will depend on the number of patients ultimately enrolled.

Retrospective component: Data will be collected from patients who underwent thoracoscopic surgery at the Department of Thoracic Surgery, Tongji Hospital, Tongji Medical College, Huazhong University of Science and Technology, between January 2024 and December 2024, with a total of 2,000 cases included.

Prospective component: Based on previous similar studies, the anticipated sample size is approximately 50–100 patients. Sample size calculation will be performed using MedCalc software.

Statistical parameters for sample size calculation: Significance level (Type I error,  $\alpha$ ) = 0.01; Power (1 – Type II error,  $1-\beta$ ) = 0.90; Area under the ROC curve (AUC, AZ) = 0.85; Ratio of negative to positive groups = 0.176.

The calculation results are summarized as follows:

		Significance level (Type I error, $\alpha$ )			
		0.20	0.10	0.05	0.01
Power (1- $\beta$ )	0.20	14+3	20+4	27+5	42+8
	0.10	18+4	25+5	32+6	48+9
	0.05	21+4	29+6	37+7	54+10
	0.01	29+6	38+7	46+9	66+12

Based on calculations performed using MedCalc software, the required total sample size for this study is 57 patients. To account for potential attrition during the study, such as loss to follow-up or incomplete data, an additional 10% of participants will be included. Consequently, for each type of thoracic surgery, 63 patients will be enrolled, resulting in a total of  $63 \times 4 = 252$  patients for the study.

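### The AUC that sizes the prospective part has no defined predictor, outcome or positive group, and the only planned AUC is for ultrasound parameters that are not collected

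*Protocol*

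**What the plan says.** **Analysis.** Under Descriptive statistics, the diagnostic-evaluation paragraph plans an AUC, when appropriate, that "will be calculated to assess the predictive value of ultrasound parameters". No other AUC is planned. Data Collection and Statistical Analysis limits the data to what is listed earlier: "The variables to be recorded are as previously described".

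**Data and aims.** Study Design and the two parts of Study Procedures list MMP3, blood counts, inflammatory markers, other laboratory tests, vital signs, cough and pain scores, bowel recovery, hospital stay and 30-day complications. None is an ultrasound measurement. Elsewhere ultrasound appears only as guidance for the block. The biomarkers are to be studied "to determine their clinical relevance in predicting prognosis and postoperative recovery", and the prospective section plans to "Evaluate the association between PVB and MMP3 levels with postoperative thoracic complications".

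**Sample size.** Sample Size Estimation uses alpha 0.01, power 0.90, "Area under the ROC curve (AUC, AZ) = 0.85" and "Ratio of negative to positive groups = 0.176". This gives 48+9 = 57. After a 10% addition, "for each type of thoracic surgery, 63 patients will be enrolled", and 63 × 4 = 252. The same section first says that "the anticipated sample size is approximately 50–100 patients".

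**The concern.** The analysis and the sample size should describe the same quantity, and here they cannot be matched. The planned AUC has a predictor that is not collected. The AUC behind the sample size has no predictor, no outcome and no definition of positive. The calculation is applied to each surgery type, yet no AUC by type is planned. The anticipated 50–100 patients would fit one pooled AUC (57, or 63 with losses) but not 252.

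Two things are at stake. First, any marker, outcome or subgroup could later be presented as the one the study was powered for. Second, a reader cannot tell whether 57 is enough, because the requirement depends strongly on the share of positives. A ratio of 0.176 means roughly 85% positive, which is hard to square with a 30-day complication, the outcome the prospective section links to MMP3.

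**Working it through.** **Inputs from Sample Size Estimation:** AUC A = 0.85, alpha 0.01, power 0.90, negative-to-positive ratio r = 0.176. **Assumptions, because the protocol is silent:** null AUC 0.5 and a two-sided test. Both are supported by the match below.

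**Formula** (Hanley–McNeil, large sample):

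- n_pos = [z(0.995)·√V0 + z(0.90)·√V1]² / (A − 0.5)², and n_neg = r·n_pos
- V0 = (1 + 1/r)/12
- V1 = a/r + b, with a = A/(2 − A) − A² = 0.73913 − 0.7225 = 0.01663 and b = 2A²/(1 + A) − A² = 0.78108 − 0.7225 = 0.05858

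**Step 1: reproduce the protocol's figure.** With r = 0.176:

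- V0 = 0.5568 and V1 = 0.1531
- n_pos = (2.5758 × 0.7462 + 1.2816 × 0.3912)² / 0.1225 = 47.95
- n_neg = 0.176 × 47.95 = 8.44

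Rounded up, this is 48+9 = 57. The same formula returns all 16 cells of the protocol's table. The 48 are therefore the positives, and the implied positive share is 1/1.176 = 85%.

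**Step 2: vary the share of positives.** Suppose positive means a 30-day complication with incidence p, so r = (1 − p)/p. The Background's 8–40% is taken as an assumed range. Enrolment follows the protocol's own rule (× 1.1, rounded up; 57 gives 63).

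| Incidence p | r | n_pos + n_neg (unrounded) | Evaluable per type | Enrolled per type | Four types | Power with 57 |
|---|---|---|---|---|---|---|
| 8% | 11.5 | 9.68 + 111.38 | 122 | 135 | 540 | 45% |
| 15% | 5.67 | 10.32 + 58.48 | 70 | 77 | 308 | 81% |
| 20% | 4.0 | 10.84 + 43.36 | 55 | 61 | 244 | 92% |
| 40% | 1.5 | 13.76 + 20.64 | 35 | 39 | 156 | >99% |
| Protocol (85%) | 0.176 | 47.95 + 8.44 | 57 | 63 | 252 | 91% |

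Power is Φ{[0.35·√n_pos − z(0.995)·√V0]/√V1} with n_pos = 57p.

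**Step 3: where 90% power is lost.** Setting power to 0.90 and solving for p:

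- 57 evaluable per type: 18.8%
- 63 per type, if none is lost: 16.6%
- pooled, 252 × 0.9 ≈ 227 evaluable: 4.1%

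Pooled power is at least 99.8% across 8–40%.

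**Precision.** A finite-sample version of the same variance gives 58 for the protocol's case and 125, 74 and 38 at 8%, 15% and 40%, with power of 44% and 80% for 57 patients at 8% and 15%. The conclusions do not change. At 8%, 57 patients contain only about 4.6 positives (57 × 0.08), so the low-incidence figures are rough under any normal approximation.

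**The case against.** The case for leaving this alone has several parts.

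- **The size is only indicative.** The section opens by saying that the final number depends on enrolment, and the stated objective concerns the block and complications, which the 2,000 retrospective cases also address. This lowers the stakes, but the section still commits to 63 patients per type, derived from this AUC alone.
- **The AUC is optional, and other methods cover prediction.** Correlation, logistic and Cox models are planned for associations and predictive effects, so the biomarker aim does have an analysis. That is true, but none of those is what the sample size was calculated for. If the AUC is optional, the size rests on an optional analysis of data not collected.
- **Missing detail may sit in a statistical analysis plan.** This holds for finer specification. It does not hold for naming an uncollected predictor, or for fixing enrolment on an undefined quantity; both are in the protocol itself.
- **85% is not a contradiction.** This stands. Positive is undefined and may mean something other than a complication. The 8–40% range describes surgery under general anaesthesia worldwide, while the composite here is broad and follows thoracic surgery. The 85% is doubtful, not impossible.
- **The power loss is conditional.** This also stands. From 20% to 40% incidence the plan needs fewer than 57 per type, and a pooled AUC is amply powered.

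**Conclusion.** The concern holds and should be fixed before the data are analysed. The unconditional part needs no assumption: the planned AUC cannot be computed from the listed variables, the AUC behind 57, 63 and 252 is undefined, and 50–100 and 252 stand unreconciled in the same section.

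The power shortfall is conditional. The stated 90% fails only if the outcome is 30-day complications, the AUC is estimated separately for each surgery type, and incidence is below about 19%. Under those conditions the need rises to about 70 evaluable patients per type at 15% and 122 at 8%, against 57. If about 85% truly are positive for the intended outcome, 57 is right. An inverted ratio (15% positive) is a plausible explanation, but nothing in the protocol proves it.

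**What to change.** 1. **Diagnostic-evaluation paragraph:** replace the ultrasound parameters with a marker that is collected, set against a named outcome. MMP3 against the 30-day complications of the prospective section is the natural candidate, for the sponsor to confirm.
2. **Sample Size Estimation:** name the same predictor and outcome, define positive, and say whether the AUC is per surgery type or pooled, so that 50–100 and 252 agree.
3. **Ratio:** replace 0.176 with (1 − p)/p for the expected share p of positives and give the source of p. If 85% is intended, say for which outcome and why. Then restate the required size, or the power given by 57 per type or about 227 pooled.
4. **Optional:** add a sentence that 57 and 252 size this AUC and not the comparison of patients with and without the block.

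The cost is wording in two sections and one rerun of the MedCalc calculation. The markers and complications are already to be collected. Enrolment changes only if the AUC is per type and the expected incidence calls for it; with a pooled AUC, 252 can stay.
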